Aim #3: To determine if active TENS alters pain processing in women with fibromyalgia and if improvement in clinical symptoms correlates with normalization of pain processing physiology. We will evaluate change in these physiologic parameters in responders versus non-responders as assessed clinically.

Aim #4: To determine if PROMIS is a useful instrument for assessing outcome for fibromyalgia by comparing to the revised version of the fibromyalgia impact questionnaire (FIQ-R).

Healthy Control Aims:

Aims:

Physically active women with fibromyalgia will have a similar phenotype (pain thresholds and conditioned pain modulation) and cytokine profile to physical active women without pain; conversely sedentary women with fibromyalgia will have a similar phenotype and cytokine release profile to sedentary women without pain.

Aim #5 will perform quantitative sensory testing to profile excitability and central inhibition in individuals with fibromyalgia and healthy controls; both sedentary and physically active individuals will be recruited in each cohort.

Aim #6 will examine for cytokine release profiles in immune cells (monocytes) from the sedentary and physically active individuals with and without fibromyalgia.

Study Synopsis

Protocol Title	Fibromyalgia Activity Study with TENS (Transcutaneous Electrical Nerve Stimulation)
Protocol Number	
Name of Sponsor	Funded by NIH NIAMS Performed at University of Iowa, Vanderbilt University
Investigational Product	TENS (Transcutaneous Electrical Nerve Stimulation) TENS is a non-pharmacological agent which delivers electrical stimulation by a battery operated device via electrodes placed on the skin. TENS is considered to be a safe, inexpensive and non-invasive modality used to treat a variety of acute and chronic pain conditions.
Phase of Development	Phase II Clinical Trial
Purpose of Study	The primary aim of the study is to test the effect of the long-term use of TENS on movement-related pain as measured by a numeric rating scale (NRS) during six minute walk test (6MWT) in women with fibromyalgia with random assignment to three treatments: standard care (No TENS), placebo TENS and active TENS.
Indication	Women with Fibromyalgia, ages 18-70
Number of Centers	The study will be conducted at 2 study sites: University of Iowa and the Vanderbilt University
Study Duration	5 years

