Objectives	
Aim #1: The primary aim of the study is to test the effectiveness of repeated TENS use on movement-related pain in people with fibromyalgia with random assignment to three treatments: standard care, placebo TENS and active
 
Aim #2: A secondary aim will test if pain reduction by TENS results in a concomitant decrease in fatigue and fear of movement, and an increase in function and quality of life. Outcome measures will include physical function by directly assessing daily activity with an accelerometer, as well as performing specific functional tasks
 
Aim #3: To determine if active TENS alters pain processing in women with fibromyalgia and if improvement in clinical symptoms correlates with normalization of pain processing physiology. We will evaluate change in these physiologic parameters in responders versus non-responders as assessed clinically.
 
Aim #4: To determine if PROMIS is a useful instrument for assessing outcome for fibromyalgia by comparing to the revised version of the fibromyalgia impact questionnaire (FIQ-R).

Study Design	This is a phase II randomized, double-blind, placebo controlled multi-center clinical trial. The initial phase of the study will randomly allocate subjects to receive active TENS, placebo TENS or standard care (No TENS). After participating in the 1 month random assignment, all subjects will receive active TENS for 1 month. The subjects will make 4 visits to the clinic.

Subject Population	Females with fibromyalgia.
Inclusion Criteria	
 • Participants will be 18 to 70 years of age • Women may participate in the study • Diagnosis of Fibromyalgia by 1990 ACR criteria • History of cervical or lumbar pain with fibromyalgia (this is expected in all patients since axial pain is required for diagnosis) • Current stable treatment regimen for the last 4 weeks and projected stable treatment regimen for the next 2 months. • English speaking

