Exclusion Criteria	
 • Current or history of cardiovascular, pulmonary, neurological, endocrine, or renal disease that would preclude the involvement in the study. • TENS use in the last 5 years • Pacemaker • Uncontrolled blood pressure or diabetes • Neuropathic pain condition • Systemic autoimmune disorder (Lupus, PMR, RA, Psoriatic arthritis) • Spinal fusion – cervical or lumbar • Metal implants in the spine • Severe skin allergy to adhesive • Allergy to nickel • Pain less than 4 • Pregnancy • Epilepsy • Change in or new drug or treatment program within the last month or in the next 2months, i.e. must have a stable treatment plan • Unstable medical or psychiatric condition which in the opinion of the investigator could compromise the subject’s welfare or confound the study results
Planned Sample Size	Final sample size of 264 subjects divided into 88 subjects per group. We will recruit 316 subjects based on a 20% projected attrition.
Randomization	Patients will be randomly allocated on the second visit after a re-assessment of eligibility. We will use a permuted block schedule, stratified by site. The randomization schedule will be implemented using SAS v9.2 PROC PLAN, creating blocks of size 6 for each of the strata factors.
Study Device Dosage and Administration	
FDA Summary of Empi Select TENS Unit: TENS is a non-pharmacological agent which delivers electrical stimulation by a battery operated device via electrodes placed on the skin. TENS is considered to be a safe, inexpensive and non-invasive modality used to treat a variety of acute and chronic pain conditions.
 
510(k) Summary for 300 PV Complete Electrotherapy Systems 1. Manufacturer Empi [name]

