	
Contact Person: [name] [contact] Date Prepared: April 2, 2002
 
2. Device Name Proprietary Name: 300 PV Complete Electrotherapy System Common/Usual Name: Electrical Muscle and Nerve Stimulator Classification Names: Powered Muscle Stimulator, Transcutaneous Nerve Stimulator, interferential Current Stimulator, External Neuromuscular Functional Stimulator
 
3. TENS Parameters: Active and Placebo Units
 
 • TENS Frequency – 10 to 100 Hz, SMP mode • TENS Pulse Width - 200 µs • TENS Intensity - Maximal tolerable intensity • Duration: 2 h per day during activity. The 2 h may be broken into smaller segments of time with a minimum of 30 minutes. • Administration - Daily • TENS Location: TENS electrode on the skin will be a 4 x 7 butterfly electrode to the cervical and lumbar region. • Placebo TENS Unit - The placebo TENS unit will deliver current for 45s ramping to 0 in the last 15s.

Study Summary
	
This is a phase II randomized, double-blind, placebo controlled multi-center clinical trial involving a device, TENS, to assess the efficacy of TENS on pain with movement over a 1 month period in subjects with fibromyalgia. After participating in the 1 month random assignment, all subjects will receive active TENS for 1 month. Subjects will receive a phone call weekly from the study coordinator regarding progress.
 
 • Screening: Telephone screen for eligibility for the study • Assessor – performs baseline and all testing except TENS allocation and TENS home instruction. The assessor is blinded to TENS treatment. • TENS Allocator – performs TENS allocation, home instructions and questions regarding TENS

Demographic and Outcome Measures
	
 • Consent • Health History/Demographic • Vital Signs • Confirmation of ACR 1990 Criteria for FM/Tender Point Exam • 2010 ACR Criteria • NRS Rest Pain, Rest Fatigue, Movement Pain, Movement Fatigue • BPI • PROMIS • FIQR • SF-36 • MAF • TSK • IPAQ • PSQI • PSEQ • PCS

	
 • Global Impression of Change • Accelerometry (Actigraph) • 6MWT • STS • FR • PPT • CPM • TENS

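### One stated block size of 6, a no-device arm and no described concealment: up to about 29% of TENS versus No-TENS allocations could be known in advance to a fully informed eligibility decision-maker

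*Combined protocol and SAP*

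**What the plan says.** The Randomization entry of the Study Synopsis gives the method: "We will use a permuted block schedule, stratified by site". The SAS schedule is described as "creating blocks of size 6 for each of the strata factors". No other block size and no random variation in size is mentioned. Site is the only stratum, and under Number of Centers, "The study will be conducted at 2 study sites".

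On timing, the same entry says: "Patients will be randomly allocated on the second visit after a re-assessment of eligibility". The schedule section adds that participants count as enrolled at visit 1 and have their eligibility reviewed again at visit 2. The exclusion criteria include one, for unstable medical or psychiatric conditions, that turns on the investigator's opinion. Treatment must also be projected to stay stable over the next 2 months.

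The three arms are active TENS, placebo TENS and standard care without a device. The Planned Sample Size entry has equal groups: "Final sample size of 264 subjects divided into 88 subjects per group".

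The Study Summary entry separates two roles. Of the assessor it says: "The assessor is blinded to TENS treatment". The TENS Allocator "performs TENS allocation, home instructions and questions regarding TENS". The documents do not say how the list is held or released, whether site staff know the block size, or how the absence of a device is kept from the assessor.

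**The concern.** With equal allocation, each block of 6 holds two No-TENS places and four TENS places. Someone who knows the block size, and has followed in order which earlier participants at the site received a device, can count down the block. Once the remaining places are all of one kind, the next allocation is known before it is made.

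That matters because an eligibility decision comes immediately before allocation and leaves some room for judgement. If the person making it could foresee the next allocation, the choice of whom to randomise could depend on the arm. Participants in the standard-care arm could then differ from those given a device for reasons other than treatment. Bias of that kind enters before baseline and cannot be reliably removed by analysis. Two of the three planned pairwise comparisons under Aim #1 involve standard care.

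**Working it through.** The documents give no predictability figure to reproduce, so this is a direct calculation.

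**Inputs**
- Block size 6, one size only (Randomization).
- Ratio 1:1:1, inferred from 88 per group (Planned Sample Size). Each block then holds 2 No-TENS (N) and 4 TENS (T).
- Assumption: the observer knows the block size and where blocks start, and sees every earlier TENS/No-TENS allocation at the site in order.

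**Certain allocations per block.** A place is certain when all places left in the block are of one type. The expected number per block is the sum over j of P(the last j places are all the same type):
- j = 1: 1 = 15/15
- j = 2: both T, (4/6)(3/5) = 6/15; both N, (2/6)(1/5) = 1/15; total 7/15
- j = 3: all T, (4·3·2)/(6·5·4) = 3/15
- j = 4: all T, (4·3·2·1)/(6·5·4·3) = 1/15

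Sum = (15 + 7 + 3 + 1)/15 = 26/15 = 1.73 places. As a share of the block, (26/15)/6 = 28.9%. By place in the block, the chance of certainty is 0, 0, 6.7%, 20%, 46.7% and 100%.

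**Split by type**
- Certain TENS: (10 + 6 + 3 + 1)/15 = 20/15; divided by 6, 22.2%.
- Certain No-TENS: (5 + 1)/15 = 6/15; divided by 6, 6.7%.

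**Best guess.** Always guessing the type with more places left is right with probability 2/3 at each of places 1 to 3, 11/15 at places 4 and 5, and 1 at place 6. The mean is (3 × 2/3 + 2 × 11/15 + 1)/6 = 4.467/6 = 74.4%. Always guessing TENS, with no information, gives 4/6 = 66.7%.

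**Scale.** If all 316 recruits were randomised in complete blocks, 0.289 × 316 is about 91 allocations, of which 0.067 × 316, about 21, would be certain No-TENS. With 158 per site (an assumed equal split) and an incomplete last block, simulation gives 28.5%.

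**Other observers**
- Someone who cannot see earlier allocations: 0% certain.
- Someone who also knows active from placebo for earlier participants: 1 + 3 × (1/15) = 1.2 of 6 places (20%) certain as to exact arm. Enumeration gives a best guess of 56.1%, against 33.3%.

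**Effect of varying the block size.** A simulation (300 runs of 300 allocations) chose sizes at random with equal probability. The observer knew the set of possible sizes but not the current one. The share of TENS/No-TENS allocations that were certain:

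| Block sizes | Certain share |
|---|---|
| 6 only (check on the exact 28.9%) | 29.0% |
| 3 and 6 | 10.1% |
| 6 and 9 | 5.2% |
| 3, 6 and 9 | 4.0% |

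The gain comes from hiding the current size. Known fixed blocks of 3 would be worse than the plan (44.4% certain), and known fixed blocks of 9 only somewhat better (21.4%).

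**The case against.** A reader might infer that site staff in general would know 29% of allocations, since anyone can see who leaves without a device. The documents do not support that. They state that the assessor is blinded and give allocation and home instruction to a separate role. The TENS Allocator plainly sees past allocations, but nothing says that this person, or anyone else who sees them, decides visit 2 eligibility. The order-of-testing table has a colour key for who performs each step; the colours are lost in the text used here, so the point cannot be settled from it. A reader with the coloured table should check it. This objection stands, and it makes the 29% conditional.

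Other points have weight:
- Most of the certain cases are TENS, which still leaves active versus placebo unknown. The best guess improves by only 7.7 percentage points (74.4 − 66.7).
- The 20% exact-arm figure needs knowledge that the double-blind design is meant to withhold, so it should not be read as a finding about this trial.
- Most eligibility criteria are factual and were already applied at visit 1, so the room for selection is limited.
- A single block size is a legitimate method, and 6 is twice the smallest possible block for three equal arms.

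Against this, the blinding of the assessor is asserted without saying how a no-device arm is hidden, and no concealment procedure is given that would rule the route out. The improvement is also more than taste: it cuts the certain share about sevenfold (28.9/4.0).

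**Conclusion.** The point holds as a conditional, low-severity design improvement. Up to about 29% of TENS versus No-TENS allocations could be known in advance (22.2% certain TENS, 6.7% certain No-TENS). This rests on complete 1:1:1 blocks and on the visit 2 eligibility decision being made by someone who knows the block size and sees earlier allocations at the site. For anyone who does not see them, the figure is zero.

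The exposure is mainly in the two contrasts with standard care; seeing who has a device does not separate active from placebo. The documents do not show that selection occurred, and no bias in a treatment effect has been estimated here.

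**What to change.** For allocations not yet made:
- Generate the schedule with randomly varying block sizes within site, for example 3, 6 and 9, and keep the sizes out of documents held at the sites.
- Have visit 2 eligibility confirmed and recorded before the allocation is released, by someone who does not see earlier allocations.
- State in the protocol who that person is and how the list is held and released.

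The first step alone brings the certain share to about 4%, even if the set of possible sizes becomes known.

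The programming cost is a few lines in the SAS procedure already named. The statistical cost is a slightly larger possible imbalance at the end of each site's list: two arms can differ by at most 3 in an unfinished block of 9, against 2 in a block of 6. The documents do not give enrolment status. If a schedule is already in use, its unused part must be replaced under version control, which costs more than a change before the start. If no allocations remain, only the reporting of who decided eligibility and how allocation was concealed can still be improved.

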Criteria for Evaluation	
Primary Efficacy Endpoint:
 
 • Pain with movement (NRS) during 6MWT 
Secondary Efficacy Endpoints:
 
 • Health History/Demographics • Vital Signs • Confirmation of ACR 1990 Criteria for FM/Tender Point Exam • 2010 ACR Criteria • NRS Rest Pain, Rest Fatigue, Movement Pain, Movement Fatigue • BPI • PROMIS • FIQR • SF-36 • MAF • TSK • IPAQ • PSQI • PSEQ • PCS • Global Impression of Change • Accelerometry • 6MWT • STS • FR • PPT • CPM • TENS • Blinding
Statistical Methods	
 • Continuous variables will be summarized with descriptive statistics (n, mean, standard deviation, standard error, median, first and third quartiles, and minimum and maximum). • Categorical variables will be described with counts and percentages. The endpoints (VAS, BPI, PPT, CPM, and 6MWT, STS, FR and accelerometry measures) will be treated as continuous variables as well as scores from questionnaires (FIQR, SF-36, MAF, and TSK, PROMIS). • Changes from initial measurement to one month after randomization will be calculated for each of these endpoints. Changes in outcomes and percent changes in outcomes will be treated as continuous variables and will be summarized with descriptive statistics. Outcomes will be summarized by visit, as change from initial measurement, and percent

	
change from initial measurement. Continuous endpoints may also be categorized into discrete variables when appropriate. Shift tables may be utilized to investigate shifts in outcome categories from baseline to one month after randomization. SAS v9.2 or higher will be used for all analyses and a significance level of 0.05 will be used for all statistical tests. In the case that endpoints are found to be non-normal, appropriate transformations will be employed and non-parametric tests may be used

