The subjects will attend four visits for the FAST study. Each session will last 2-4hours for testing. Testing measures will include health history/demographics questionnaire, pain measures, multidimensional questionnaires, functional assessments and quantitative sensory testing. Home activities will include accelerometry, medication logs, TENS unit.

A general outline of measures and visits is given in Table 1, the order of testing is given in Table 2, and a list of equipment, forms, and measures is given in Table 3.

Subjects are considered enrolled after consent and meeting eligibility criteria on Visit 1. They will be randomized to treatment on Visit 2 and they will be re-reviewed for eligibility criteria.

It is expected that Visit 1 will take no more than 1h, Visit 2 will take 2-3 hours, Visit 3 will take 3-4 hours, and Visit 4 will take 2-3 hours.

Table 1: Schedule of tests and measures

Measurement	Instrument	Visit (V)	Construct and General Information	Reliability	Validity-Cronbach's-Alpha (α)	Reference
Pain and Fatigue	NRS	V1 V2 V3 V4	Self report of pain and fatigue intensity on 0-10 vertical scale;	ICC=0.71-0.99	0.71-0.78	^{51, 52}

			Pain and fatigue intensity at rest and movement			
Multidimensional Questionnaires	BPI	V2 V3 V4	Pain intensity and pain interference with activities; 15 questions	r=0.57	0.85-0.88	⁵³
	HH/Demo	V1	Demographic; Review of past medical history	NA	NA	NA
	FIQR	V1 V2 V3 V4	Disease specific questionnaire; 21 questions	r=0.88	0.69-0.88	⁵⁴
	GIC	V3 V4	Perception of change	r=0.87	ICC=0.9	⁵⁵
	IPAQ	V2 V3 V4	Self report of activity level among adults; Short form	Spearman's $\rho = 0.80$	Spearman's $\rho = 0.78$	⁵⁶
	MAF	V2 V3 V4	Fatigue questionnaire; 16 questions; 4 dimensions of fatigue	0.93	r=0.62- 0.84	⁵⁷
	PCS	V2 V3 V4	Pain Catastrophizing scale; 13 items pain	Total Cronbach's alpha 0.95	0.42	⁵⁸
	PSEQ	V2 V3 V4	Pain Self Efficacy; 10 items; confidence in performing activities with chronic pain	r=0.73	0.67 - 0.84	⁵⁹
	PROMIS	V2 V3 V4	Quality of Life; NIH patient reported outcome measurement system	NA	NA	NA
	PSQI	V2 V3 V4	Pittsburgh Sleep quality index; 19 items sleep disturbance and sleep habits	0.80	R= 0.07 to 0.80	⁶⁰
	SF-36	V2 V3 V4	General Quality of Life; 36 items	r=0.85	0.97	⁶¹
	TSK	V2 V3 V4	Fear of pain with movement; 17 items	r=0.64-.99	r=0.70-0.81	⁶²⁻⁶⁴
Function	6MWT	V2 V3 V4	Function; Walk test for endurance	ICC[2,1]=0.95-0.97	r=-/63-0.79	²⁶

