	FTSTS	V2 V3 V4	Function; Measure of leg strength	ICC 1 >0.95	r=0.59-0.88 LBP r=0.46-0.76 Control	^{65, 66}

	FR	V2 V3 V4	Function; Measure of balance	r=0.95	r=0.7	^{27, 67}
	Actigraph: Actisleep+	Week Before V2 V3 V4	Function: Activity and Sleep Accelerometer worn on wrist	NA	NA	NA
Quantitative Sensory Testing	PPT	V2 V3 V4	Deep mechanical hyperalgesia; Pressure Pain Thresholds	r=0.79-0.94 ICC = 0.85- 0.99 Test- retest=0.70 -0.94	Significant differences between healthy and RA subjects (p<0.05)	⁶⁸⁻⁷²
	CPM (DNIC)	V2 V3 V4	Central Inhibition	Face validity as the same test in animals activates descending inhibitory pathways		

*Table 3:
List of
equipment,
form per
test and
measure*

Order of Testing FAST June 2014

Order of Testing FAST June 2014							
Key:							
Blue= Assessor	Black= Subject	Red= TENS Allocator					
Session 1	Session 2		Session 3		Session 4		
Pre-consent Eligibility Screen	NRS Rest - Pain,Fatigue		NRS Rest - Pain,Fatigue		NRS Rest - Pain,Fatigue		
Reimbursement Form	FIQR		FIQR		FIQR		
Consent	Medication Log		Medication Log		Medication Log		
Confirmation of Consent	Eligibility		Adverse Event Screen		Adverse Event Screen		
Adverse Event Screen	Adverse Event Screen	Download Actigraph Data	Questionnaires (4-5) 1990 & 2010 ACR	Download Actigraph Data	Questionnaires (4-5) 1990 & 2010 ACR	Download Actigraph Data	
Medication Log	Questionnaires (4-5)		6MWT	Download/Record TENS Data	6MWT	Download/Record TENS Data	
Health History	6MWT		FTSTS		FTSTS		
NRS Rest - Pain,Fatigue	FTSTS		FR		FR		
FIQR	FR		PPT		PPT		
Height, Weight	PPT		TENS Treatment 1	5 min TENS Check	TENS	5 min TENS Check	
1990 FM ACR	TENS	5 min TENS Check	Questionnaires during TENS(4-5)		Questionnaires during TENS(4-5)		
2010 FM ACR	Questionnaires during TENS(4-5)		NRS Rest - Pain,Fatigue		NRS Rest - Pain,Fatigue		
Eligibility/Review	NRS Rest - Pain,Fatigue		PPT		PPT		
TENS Tolerance Test	PPT		6MWT (NRS Mvmt Pain, Fatigue, BORG)		6MWT (NRS Mvmt Pain, Fatigue, BORG)		
Actigraph	6MWT (NRS Mvmt Pain, Fatigue, BORG)		FTSTS (NRS Mvmt Pain, Fatigue)		FTSTS (NRS Mvmt Pain, Fatigue)		
Adverse Event Screen	FTSTS (NRS Mvmt Pain, Fatigue)		FR		FR		
Blood Draw	FR		CPM		CPM		
	CPM		Blinding question		GIC	TENS off	
	TENS Home		Turn off TENS		Survey		
	Actigraph Home		GIC		Survey		
	AES		Blinding question				
	Record and Clear Data		Debriefing (Active may be done)				
			Record/Clear Data				
			TENS Treatment 2	5 min TENS Check			
			NRS Rest - Pain,Fatigue				
			PPT				

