			6MWT (NRS Mvmt Pain, Fatigue, BORG)				
			FTSTS (NRS Mvmt Pain, Fatigue)				
			FR				
			CPM				
			TENS Home				
			Actigraph Home				
			AES				
			Record and Clear Data				

Table 3: List of equipment, form per test and measure

Area	Form	Visit	Equipment: Clipboards, Pens, Computer/Form
	Screening Log	Pre Visit	Computer/Form
Surveys	Consent	1	Computer/Form
	Health History/Demographic	1	Computer/Form
	Diagnostic Confirmation	1	Computer/Form
	Eligibility Confirmation	1, 2	Computer/Form
	FIQR	1,2,3,4	Computer/Form
	MAF	2,3,4	Computer/Form
	TSK	2,3,4	Computer/Form
	Medication	1,2,3,4	Computer/Form
	SF-36	2,3,4	Computer/Form
	PROMIS	2,3,4	Computer/Form
	IPAQ	2	Computer/Form
	PSQLI	2	Computer/Form
	PSEQ	2	Computer/Form
	PCS	2	Computer/Form
	Blinding Question Researcher and Subject	3	Computer/Form
	Global Impression of Change	3, 4	Computer/Form
Pain	NRS	1,2,3,4 Previsit 2,3,4	Computer/Form
	BPI	2,3,4	Computer/Form
Fatigue	NRS, BORG CR10	1,2,3,4	Computer/Form
QST	PPT (C,L, Ant Tib)	2,3,4	Algometer, Form, Marker, Alcohol swab
	CPM	2,3,4	Bucket, thermometer, Water, Ice, Towel, Form
Function	6MWT	2,3,4	Timer, Form, Distance Measurement, Pulse Oximeter, BP Cuff, Sphygmometer
	FTSTS	2,3,4	Timer, Form, Chair with arms
	Functional Reach	2, 3,4	Yardstick, Form
	Accelerometry	1,3,4	Actigraph, home tracking, initialization & instruction sheet
TENS	TENS Trial	1	TENS, Electrodes, Batteries, Lead
	TENS Treatment at Visit	2,3,4	TENS, Lead wires, Electrodes, Batteries, Participant Handbook
Handbooks	Participant Assessor	1,2,3,4	Handbook

Data Analysis Plan

Aim	Visit (V)	Measures	Statistical Plan
General Considerations	V1 V2 V3 V4	All outcome measures: Pain NRS rest and movement, Fatigue NRS rest and movement, BPI, PPT, 6MWT, FTSTS, FR, CPM, Accelerometry FIQR, SF-36, TSK, GIC, PROMIS, MAF,	
 • Descriptive Statistics • n, mean, standard deviation, standard error, median, first and third quartiles, minimum, maximum • Outcomes summarized by visit • Changes from visit to baseline; shift tables may be used to investigate shifts from visit 1 to visit 3 • • If variables not normally distributed, non-parametric tests will be used

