Aim #1	V3-V2	Pain NRS with movement (6MWT and FTSTS) for the treatment groups: active TENS, placebo TENS or standard care	
 • Linear mixed model analysis (LMM) for repeated measures with treatment group, time (V3-V2) and treatment group*time interaction as fixed effects. • Post-hoc pair wise comparison of mean change between all three treatment groups • p-values adjusted using Bonferroni method to account for the number of tests • Potential confounders include BMI, age, race, ethnicity, educational attainment, marital status, TENS dose/intensity, change in opioid status, medication intake, rescue medications; If there are differences between potential confounders, we will include covariates
Aim #1 Intention to Treat (ITT)	V3-V2	Pain NRS with movement (6MWT and FTSTS) for the treatment groups: active TENS, placebo TENS or standard care	
 • Intention to treat (ITT) analyses using all available data for all randomized participants will be used • If there are missing data, missing at random (MAR) LMM will be used. Sensitivity analysis will be performed using pattern mixture models since data cannot be determined if it is MAR or missing not at random (MNAR). Multiple imputation will be used for sensitivity analysis by imputing from a non-random pattern mixture model • Modified ITT (mITT) will be conducted to account for subjects who did not achieve adequate dose (based on previous work, 5% of subjects randomized to active TENS

			are expected to not achieve adequate dose). This will be limited to those who achieved at least one adequate intensity dose ^{73, 74} .
Aim #2	V3-V2	Primary: Fear of movement scores. Secondary: changes in function, fatigue, resting pain, use of rescue medications, accelerometry and quality of life questionnaires.	
 • Comparison between the randomized groups will be performed as described in Aim #1. • Additional analysis using the change in fatigue, fear of movement, function, resting pain measures and quality of life as dependent variable in linear regression models, associations between these outcomes and changes in pain values will be investigated.

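### FIQR, resting pain and resting fatigue have two pre-randomisation values, but the specified arm comparison uses only visit 2 and does not adjust for it

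*Combined protocol and SAP*

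**What the plan says.** **Collection.** Table 1 schedules "FIQR V1 V2 V3 V4" and lists the pain and fatigue NRS at the same four visits. In the Order of Testing, "NRS Rest - Pain,Fatigue" and FIQR appear in Session 1 ahead of the "TENS Tolerance Test". They are the first two items of Session 2, ahead of the eligibility check and any TENS at that visit. The Synopsis (Randomization) says "Patients will be randomly allocated on the second visit after a re-assessment of eligibility", so both sets of values precede allocation. Movement NRS is not listed in Session 1, and Table 1 schedules TSK from visit 2. Table 3 gives the NRS visits as "1,2,3,4 Previsit 2,3,4", so a further NRS before visit 2 may exist; whether it is at rest or with movement is not stated.

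**Analysis.** The Aim #1 model in the Synopsis has arm, time (visits 2 and 3) and their interaction as fixed effects. Aim #2 comparisons follow it. The Aim #2 row of the Data Analysis Plan gives V3-V2 and covers "Secondary: changes in function, fatigue, resting pain, use of rescue medications, accelerometry and quality of life questionnaires". The possible covariates listed for a secondary adjusted model do not include an earlier value of the outcome.

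**Baseline wording.** The Synopsis refers to change from an initial measurement ("Changes from initial measurement to one month after randomization will be calculated for each of these endpoints"). Its Aim #2 text opens with visit 3 minus visit 1 for fear of movement. The General Considerations row of the Data Analysis Plan runs shift tables from visit 1 to visit 3. The Aim #1 model and the Aim #1 and Aim #2 rows use visit 2.

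**The concern.** One day's resting pain or fatigue rating is noisy. In a contrast of visit 3 minus visit 2, all the noise in the visit 2 value passes into the result. The planned model estimates arm means freely at visit 2, although randomisation makes them equal in expectation. With complete data its interaction test is therefore this change-score contrast. A second pre-randomisation value is already collected and could reduce the noise, but the model has no place for it.

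Two things are at stake: precision on secondary endpoints, and the definition of baseline. For these three scores both visits hold data, so either could be taken as baseline after the results are seen. For TSK the visit 1 baseline named in the Synopsis cannot be computed at all.

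**Working it through.** The plan states no power, SD or precision for these three scores, so there is no figure of its own to reproduce.

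**Inputs.** Write r12, r13 and r23 for the correlations between visits 1, 2 and 3, with variance 1 at each visit. The documents give no between-visit correlations, so all three are assumptions. Table 1 gives reliability of 0.71-0.99 (NRS) and 0.88 (FIQR) with no retest interval. I take r12 = 0.71 and 0.88 as illustrations, r23 = 0.50 and 0.65, and r13 equal to r23 or 0.05 lower.

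**Formulas** (variance per participant in an arm comparison):
- Planned contrast, V3-V2: 2(1 - r23)
- Adjusted for V2: 1 - r23²
- Adjusted for V1 and V2 separately: 1 - (r13² + r23² - 2·r12·r13·r23)/(1 - r12²). A mixed model with arms equal at V1 and V2 and unstructured covariance gives the same in large samples.

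Example, (r12, r13, r23) = (0.71, 0.65, 0.65): planned 2 × 0.35 = 0.700; V2 only 1 - 0.4225 = 0.5775; both 1 - (0.8450 - 0.59995)/0.4959 = 0.5058.

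| r12 | r13 | r23 | Planned | V2 only | V1 and V2 | Cut vs planned | V1 beyond V2 |
|---|---|---|---|---|---|---|---|
| 0.71 | 0.50 | 0.50 | 1.000 | 0.7500 | 0.7076 | 29.2% | 5.7% |
| 0.71 | 0.45 | 0.50 | 1.000 | 0.7500 | 0.7318 | 26.8% | 2.4% |
| 0.71 | 0.65 | 0.65 | 0.700 | 0.5775 | 0.5058 | 27.7% | 12.4% |
| 0.71 | 0.60 | 0.65 | 0.700 | 0.5775 | 0.5388 | 23.0% | 6.7% |
| 0.88 | 0.50 | 0.50 | 1.000 | 0.7500 | 0.7340 | 26.6% | 2.1% |
| 0.88 | 0.45 | 0.50 | 1.000 | 0.7500 | 0.7496 | 25.0% | 0.1% |
| 0.88 | 0.65 | 0.65 | 0.700 | 0.5775 | 0.5505 | 21.4% | 4.7% |
| 0.88 | 0.60 | 0.65 | 0.700 | 0.5775 | 0.5740 | 18.0% | 0.6% |

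Adjusting for V2 alone already cuts the variance by 25.0% (r23 = 0.50) or 17.5% (r23 = 0.65). At r12 = 0.99, the top of the NRS range, with r13 = r23, V1 adds under 0.5%.

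**Why not the simple mean.**
- As a covariate, the V1/V2 mean leaves 1 - ((r13 + r23)/2)²/((1 + r12)/2). At (0.88, 0.45, 0.50) this is 1 - 0.2256/0.94 = 0.7600, which is 1.3% worse than V2 alone (0.7500).
- As the baseline of a change score it leaves 1 + (1 + r12)/2 - (r13 + r23). This beats V3-V2 only if r23 - r13 < (1 - r12)/2, which is 0.06 at r12 = 0.88. With a gap of 0.10 the variance rises from 1.00 to 1.04 (r23 = 0.50) or from 0.70 to 0.74 (r23 = 0.65), a loss of 4-6%.

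**Selection on pain.** The exclusion "Pain less than 4" does not say which pain score it refers to. A simulation put a cut-off of 4 on the resting score (assumed mean 5.5-6, SD 1.8-2, all correlations 0.5 or 0.7). V1's added gain over V2 adjustment was about 7-14%, against 11-17% without the cut-off.

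**The case against.** The strongest case against is that the last value before randomisation is a valid baseline and the planned comparison is unbiased. No primary result changes, and V1's own contribution may be close to nothing. All of that stands, and it limits the point to optional efficiency.

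Four stronger readings are tempting, and the documents do not support them:
- **That the variance would fall by a quarter if V1 and V2 were averaged.** This needs all three correlations to be equal: 1.5(1 - r)/2(1 - r) = 0.75. Nothing in the documents establishes that, and averaging can lose precision.
- **That V1 is thrown away.** Outcomes are summarised by visit. An optional Aim #4 mixed model in the Synopsis, with four time points, could use both FIQR values, although the Data Analysis Plan lists V2, V3 and V4 only. What holds is narrower: the specified arm comparison does not use V1.
- **That the sentence on initial measurement fixes the baseline of that comparison.** It introduces descriptive summaries and names no visit. The evidence is the Aim #1 model and its extension to Aim #2.
- **That both values are clean.** For resting pain this is not established. The score precedes both eligibility checks and may be selected by the pain exclusion, and the V2 values follow a tolerance test at V1. Both act before allocation, so neither biases the randomised comparison, but selection would distort within-arm change. No entry threshold is stated for FIQR or fatigue.

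FIQR is also not named under Aim #2. It is a listed secondary endpoint and an Aim #4 measure, so applying the Aim #2 model to it is an inference.

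**Conclusion.** The point holds as an optional improvement for three secondary scores. Each has two pre-randomisation values, and the specified comparison uses one of them without adjusting for it. Over the assumed grid, a model using both lowers variance by about 18-29% against the planned contrast. Adjusting for V2 supplies most of this, and V1 adds about 0-12% beyond it. These figures rest entirely on assumed correlations, V1-V2 included, and on equal variances across visits.

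The disagreement over the baseline visit does not depend on any of these assumptions and should be reconciled in any case. Movement pain during the 6MWT and TSK have no visit 1 value and gain nothing from V1. A reader should not infer that the planned analysis is biased or invalid.

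**What to change.** 1. For FIQR, resting pain NRS and resting fatigue NRS, fit visits 1, 2 and 3 in the mixed model with unstructured covariance and arms constrained equal at visits 1 and 2. Alternatively, analyse visit 3 with the visit 1 and visit 2 values as two separate covariates. Do not use the simple mean of the two.
2. State that visit 2 is the baseline for measures not taken at visit 1. Bring the Aim #2 Synopsis text, the shift tables and the initial-measurement sentence into line with this.
3. Specify that the visit 2 value of the resting NRS is the first reading of that visit, before TENS. Say whether the previsit NRS is used.
4. State which pain score the entry exclusion refers to.

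The cost is analysis-plan wording, settled before unblinded data are seen. Both values are already scheduled, so there are no new data and no added burden on participants.
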